7.6.2 Clinical Laboratory Data

Summary statistics for changes from baseline in the routine clinical laboratory measurements and prolactin concentrations will be provided. In addition, the incidence of potentially clinically relevant values identified using criteria prospectively defined in the SAP for laboratory tests will be summarized for Phases B and C. Analyses will be

Protocol 331-201-00079

performed using the Safety Sample appropriate to the trial phase. Results will be presented by treatment group (brexpiprazole +ADT versus placebo + ADT) for Phase C.

7.6.3 Physical Examination and Vital Signs Data

Physical examination findings will be listed by subject. Potentially clinically relevant results in vital signs and body weight will also be summarized.

Summary statistics for change from baseline in vital signs, body weight, and waist circumference will be provided.

7.6.4 Electrocardiogram Data

Mean change from baseline and incidence of clinically significant changes will be calculated for ECG parameters. The data will be provided for each trial phase using the appropriate Safety Sample.

For the analysis of QT and QTc data from 3 consecutive complexes (representing 3 consecutive heart beats) will be measured to determine average values. The following QT corrections will be used:

- 1) QTcB is the length of the QT interval corrected for heart rate by the Bazett formula: $QTcB = QT/(RR)0.5$, and
- 2) QTcF is the length of the QT interval corrected for heart rate by the Fridericia formula: $QTcF = QT/(RR)0.33$

Results will be summarized by visit.

7.6.5 Other Safety Data

Descriptive statistics will be provided for change from baseline to end of phase in SAS, AIMS, and BARS scores for Phases A, B and C, separately. Results will be summarized by visit. In addition, change from end of Phase B to end of Phase C in scores for the SAS, AIMS, and BARS scales will be evaluated using ANCOVA with baseline value as covariate and treatment as factor. The OC data sets will be used in the analyses of these EPS scales.

Suicidality monitored during the trial using the C-SSRS will be summarized as number and percentage of subjects reporting any suicidal behavior, ideation, behavior by type (4 types), ideation by type (5 types), and treatment-emergent suicidal behavior and ideation.

8 Management of Investigational Medicinal Product

For full details on IMP management, please refer to the IB.¹³

Protocol 331-201-00079

8.1 Packaging and Labeling

Trial medication will be provided to the investigators and the persons designated by the investigator(s) or institution(s) by the sponsor or designated agent. The IMP will be supplied as blister cards. Each blister card used in the dosing period will be labeled to clearly disclose the subject ID, compound ID, trial number, sponsor's name and address, instructions for use, route of administration, and appropriate precautionary statements.

Antidepressant therapies will be supplied as bulk drug in commercial packaging (eg, bottles) with an ancillary trial-specific label that will be positioned such that it will not obscure the original commercial label. The Sponsor reserves the right to use a generic equivalent, should any marketed antidepressant become unavailable during the course of the trial. Each ADT bottle used in the trial will be labeled to clearly disclose the bottle number, subject ID, subject's initials, protocol number, ADT drug name, the sponsor's name and address, instructions for use, route of administration, and appropriate precautionary statements. The amount of open-label ADT dispensed to a subject at each visit will be contingent upon the prescribed daily dose of ADT as well as the duration between trial visits.

8.2 Storage

The IMP will be stored in a securely locked cabinet or enclosure. Access will be limited to investigators and their designees. Neither investigators nor any designees may provide IMP to any subject not participating in this protocol.

The IMP will be stored according to the storage conditions indicated on the clinical label(s). The clinical site staff will maintain a temperature log in the IMP storage area recording the temperature at least once each working day.

8.3 Accountability

The investigator or designee must maintain an inventory record of IMP (including investigational, active control, or placebo) received, dispensed, administered, and returned.

8.4 Returns and Destruction

All used IMP containers, unused IMP, and partially-used IMP should be destroyed at the trial site(s) or at the site level in accordance with all local and national regulations.

On-site destruction will only occur after drug accountability for the IMP being destroyed has been completed by the CRA (clinical research associate). On-site destruction will be performed by both site personnel and CRA personnel. On-site Destruction Certificates

Protocol 331-201-00079

will be linked to specific drug unit ID number(s) or batch number(s) and quantities of clinical supplies destroyed at the clinical site. The original Destruction Certificates will be retained at clinical sites, and copies will be placed in the trial master file.

8.5 Reporting of Product Quality Complaints

A product quality complaint (PQC) is any written, electronic, or verbal communication by a healthcare professional, consumer, subject, medical representative, Competent Authority, regulatory agency, partner, affiliate or other third party that alleges deficiencies or dissatisfaction related to identity, quality, labeling, packaging, reliability, safety, durability, tampering, counterfeiting, theft, effectiveness or performance of a drug product or medical device after it is released for distribution. Examples include, but are not limited to, communications involving:

- Failure/malfunction of a product to meet any of its specifications
- Incorrect or missing labeling
- Packaging issues (eg, damaged, dirty, crushed, missing product)
- Blister defects (eg, missing, empty blisters)
- Bottle defects (eg, under/over-fill, no safety seal)
- Vial defects
- Product defect (eg, odor, chipped, broken, embossing illegible)
- Loss or theft of product

8.5.1 Eliciting and Reporting Product Quality Complaints

The investigator or designee must record all PQCs identified through any means from the receipt of the IMP from the sponsor, or sponsor's designee, through and including reconciliation and up to destruction, including subject dosing. The investigator or designee must notify the sponsor (or sponsor's designee) by e-mail or telephone within 24 hours of becoming aware of the PQC according to the procedure outlined below.

- Online – Send information required for reporting purposes (listed below) to [contact]
- Phone - Rocky Mountain Call Center at [name].

Identification of a PQC by the subject should be reported to the site investigator, who should then follow one of the reporting mechanisms above.

8.5.2 Information Required for Reporting Purposes

- Description of compliant

Protocol 331-201-00079

- Reporter identification (eg, subject, investigator, site, etc.)
- Reporter contact information (eg, address, phone number, e-mail address)
- ID of material (product/compound name, coding)
- Clinical protocol reference (number and/or trial name)
- Dosage form/strength (if known)
- Pictures (if available)
- Availability for return

8.5.3 Return Process

Indicate during the report of the PQC if the complaint sample is available for return. If complaint sample is available for return, return it in the product retrieval package, which will be provided by the sponsor.

It must be documented in the site accountability record that a complaint sample for a dispensed kit has been forwarded to the sponsor for complaint investigation.

8.5.4 Assessment/Evaluation

Assessment and evaluation of PQCs will be handled by the sponsor.

9 Records Management

9.1 Source Documents

Source documents are defined as the results of original observations and activities of a clinical investigation. Source documents will include but are not limited to progress notes, electronic data, screening logs, and recorded data from automated instruments. All source documents pertaining to this trial will be maintained by the investigators and made available for direct inspection by authorized persons.

Investigator(s)/institution(s) will permit trial-related monitoring, audits, IRB/IEC review, and regulatory inspection(s) by providing direct access to source data/documents by authorized persons as defined in the ICF. In all cases, subject confidentiality must be maintained in accordance with local regulatory requirements.

Protocol 331-201-00079

9.2 Data Collection

During each subject's visit to the clinic, a clinician participating in the trial will record progress notes to document all significant observations. At a minimum, these notes will contain:

- Documentation of the informed consent process, including any revised consents;
- Documentation of the investigator's decision to enroll the subject into the trial, the review of all inclusion/exclusion criteria prior to IMP administration, and confirmation of the subject's actual participation in the trial;
- The date of the visit and the corresponding Visit or Day in the trial schedule;
- General subject status remarks, including any *significant* medical findings. The severity, frequency, duration, action taken, and outcome of any AEs and the investigator's assessment of relationship to IMP must also be recorded;
- Any changes in concomitant medications or dosages;
- A general reference to the procedures completed;
- The signature (or initials) and date of each clinician (or designee) who made an entry in the progress notes.

In addition, any contact with the subject via telephone or other means that provides significant clinical information will also be documented in the progress notes as described above.

Source documents and source data will be captured electronically in this trial, and will meet the same fundamental elements of data quality (eg, attributable, legible, contemporaneous, original, and accurate) as paper records. These data will be collected into a system that is fully validated. Changes to the data will be captured by an automatic audit trail.

The trial site will be given a tablet to directly record subject data and clinical observations on electronic forms. Designated trial site staff will not be given access to the system until they have been appropriately trained. Information to be originally captured and reviewed electronically shall include details of the subject visit and the protocol-required assessments performed as a part of these visits, medical history, AEs, and concomitant medications. Because this trial is using an electronic source record as the original point of data capture, there is no additional data entry step for the trial site for data collected directly into the application - rather, the electronic source record directly populates the trial database.

Some data may be captured via paper and then entered into the eSource system. These and any other data treated in this manner will be source data verified by the trial clinical

Protocol 331-201-00079

research associate, and the location of the source data (ie, eSource, paper, or a local electronic system) will be documented before the trial start. Any changes to information in paper source documents will be initialed and dated on the day the change is made by a trial site staff member authorized to make the change. Changes will be made by striking a single line through erroneous data (so as not to obliterate the original data), and clearly entering the correct data (eg, ~~wrong data~~ right data). If the reason for the change is not apparent, a brief explanation for the change will be written in the source documentation by the clinician.

Another exception will be safety laboratory data, where the official source documentation will be considered the report issued by the analyzing laboratory.

Remote monitoring of the original electronic source record will take place, however on-site monitoring inspections will continue to take place in order to review data entry of source documentation directly captured on paper and transcribed into the system, to ensure protocol adherence, to assess trial site operational capabilities and to perform other monitoring activities that cannot be performed remotely.

At the end of the trial, the investigator must certify that the data entered on the eSource application are complete and accurate. After database lock, the investigator will receive an electronic copy of the subject data.

9.3 File Management at the Trial Site

The investigator will ensure that the trial site file is maintained in accordance with [Section 8](#) of the ICH GCP Guideline E6 and as required by applicable local regulations.

The investigator/institution will take measures to prevent accidental or premature destruction of these documents.

9.4 Records Retention at the Trial Site

Food and Drug Administration (FDA) regulations require all investigators participating in clinical drug trials to maintain detailed clinical data for one of the following periods:

- A period of at least 2 years after the date on which a New Drug Application is approved by the FDA;
- A period of 2 years after the sponsor has notified the FDA that investigation with this drug is discontinued.

The investigator must not dispose of any records relevant to this trial without either (1) written permission from the sponsor or (2) provision of an opportunity for sponsor to collect such records. The investigator will be responsible to maintain adequate and accurate electronic or hard copy source documents of all observations and data generated

Protocol 331-201-00079

during this trial including any data clarification forms received from the sponsor. Such documentation is subject to inspection by the sponsor and relevant regulatory authorities. If the investigator withdraws from the trial (eg, due to relocation or retirement), all trial-related records should be transferred to a mutually agreed-upon designee within a sponsor-specified timeframe. Notice of such transfer will be given to the sponsor in writing.

10 Quality Control and Quality Assurance

10.1 Monitoring

The sponsor has ethical, legal, and scientific obligations to follow this trial in accordance with established research principles, the ICH E6 GCP: Consolidated Guidance, and applicable regulatory requirements and local laws. As part of a concerted effort to fulfill these obligations (maintain current personal knowledge of the progress of the trial), the sponsor's monitors will visit the site during the trial, as well as communicate frequently via telephone, e-mail, and written communications. In addition, all investigators and clinical site personnel will undergo initial and ongoing training for this particular trial, and this training will be clearly documented.

10.2 Auditing

The sponsor's Quality Assurance Unit (or representative) may conduct trial site audits. Audits will include, but are not limited to, IMP supply, presence of required documents, the informed consent process, and comparison of data on the eSource application with source documents. The investigator agrees to participate with audits.

Regulatory authorities may inspect the investigator site during or after the trial. The investigator will cooperate with such inspections and will contact the sponsor immediately if such an inspection occurs.

11 Ethics and Responsibility

This trial must be conducted in compliance with the protocol, FDA regulations, ICH GCP Guideline (E6), international ethical principles derived from the Declaration of Helsinki and Council for International Organizations of Medical Science (CIOMS) guidelines, and applicable local laws and regulations. Each trial site will seek approval/favorable opinion by an IRB or IEC according to regional requirements, and the investigator will provide that documentation to the sponsor. The IRB/IEC will evaluate the ethical, scientific and medical appropriateness of the trial. Further, in preparing and handling the eSource, the investigator, sub-investigator and their staff will take measures to ensure adequate care in

Protocol 331-201-00079

protecting subject privacy. To this end, a subject number and subject identification code will be used to identify each subject.

Financial aspects, subject insurance and the publication policy for the trial will be documented in the agreement between the sponsor and the investigator.

12 Confidentiality

All information generated in this trial will be considered confidential and will not be disclosed to anyone not directly concerned with the trial without the sponsor's prior written permission. Subject confidentiality requirements of the region(s) where the trial is conducted will be met. However, authorized regulatory officials and sponsor personnel (or their representatives) may be allowed full access to inspect and copy the records, consistent with local requirements. All IMPs, subject bodily fluids, and/or other materials collected shall be used solely in accordance with this protocol, unless otherwise agreed to in writing by the sponsor.

Subjects will be identified only by unique subject numbers on the eSource. If further subject identification is required, subjects' full names may be made known to a regulatory agency or other authorized officials if necessary, subject to local regulations.

13 Amendment Policy

The investigator will not make any changes to this protocol without the sponsor's prior written consent and subsequent approval/favorable opinion by the IRB/IEC. Any permanent change to the protocol, whether an overall change or a change for specific trial site(s), must be handled as a protocol amendment. Any amendment will be written by the sponsor. Each amendment will be submitted to the IRB/IEC, as required by local regulations. Except for "administrative" or "non-substantial" amendments, investigators will wait for IRB/IEC approval/favorable opinion of the amended protocol before implementing the change(s). Administrative amendments are defined as having no effect on the safety of subjects, conduct or management of the trial, trial design, or the quality or safety of IMP(s) used in the trial. A protocol change intended to eliminate an apparent immediate hazard to subjects should be implemented immediately after agreement by the sponsor and investigator, followed by IRB/IEC notification within local applicable timelines. The sponsor will submit protocol amendments to the applicable regulatory agencies within local applicable timelines.

When the IRB/IEC, investigators, and/or the sponsor conclude that the protocol amendment substantially alters the trial design and/or increases the potential risk to the subject, the currently approved written ICF will require similar modification. In such

Protocol 331-201-00079

cases, after approval/favorable opinion of the new ICF by the IRB/IEC, repeat written informed consent will be obtained from subjects enrolled in the trial before expecting continued participation and before the amendment-specified changes in the trial are implemented.

14 Publication Authorship Requirements

Authorship for any Otsuka-sponsored publications resulting from the conduct of this trial will be based on International Committee of Medical Journal Editors (ICMJE) authorship criteria (<http://www.icmje.org/recommendations>). According to ICMJE guidelines, one may be considered an author only if the following criteria are met:

Appendix 1 Criteria for Identifying Laboratory Values of Potential Clinical Relevance

Laboratory Tests	Criteria
Chemistry	
AST (SGOT)	≥ 3 x upper limit of normal (ULN)
ALT (SGPT)	≥ 3 x ULN
Alkaline phosphatase	≥ 3 x ULN
LDH	≥ 3 x ULN
BUN	≥ 30 mg/dL
Creatinine	≥ 2.0 mg/dL
Uric Acid	
Men	≥ 10.5 mg/dL
Women	≥ 8.5 mg/dL
Bilirubin (total)	≥ 2.0 mg/dL
CPK	≥ 3 x ULN
Prolactin	> ULN
Hematology	
Hematocrit	
Men	≤ 37 % and decrease of ≥ 3 percentage points from baseline
Women	≤ 32 % and decrease of ≥ 3 percentage points from baseline
Hemoglobin	
Men	≤ 11.5 g/dL
Women	≤ 9.5 g/dL
White blood count	≤ 2,800/ mm ³ or ≥ 16,000/ mm ³
Eosinophils	≥ 10%
Neutrophils	≤ 15%
Absolute neutrophil count	≤ 1,000/ mm ³
Platelet count	≤ 75,000/ mm ³ or ≥ 700,000/ mm ³
Urinalysis	
Protein	Increase of ≥ 2 units
Glucose	Increase of ≥ 2 units
Casts	Increase of ≥ 2 units
Additional Criteria	
Chloride	≤ 90 mEq/L or ≥ 118 mEq/L
Potassium	≤ 2.5 mEq/L or ≥ 6.5 mEq/L
Sodium	≤ 126 mEq/L or ≥ 156 mEq/L
Calcium	≤ 8.2 mg/dL or ≥ 12 mg/dL
Glucose	
Fasting	≥ 100 mg/dL
Non-Fasting	≥ 200 mg/dL
Total Cholesterol, Fasting	≥ 240 mg/dL
LDL Cholesterol, Fasting	≥ 160 mg/dL
HDL Cholesterol, Fasting	
Men	< 40 mg/dL
Women	< 50 mg/dL
Triglycerides, Fasting	≥ 150 mg/dL

Protocol 331-201-00079

Appendix 2 **Criteria for Identifying Vital Signs of Potential Clinical Relevance**

Variable	Criterion Value ^a	Change Relative to Baseline ^a
Heart Rate ^b	> 120 bpm < 50 bpm	≥ 15 bpm increase ≥ 15 bpm decrease
Systolic Blood Pressure ^b	> 180 mmHg < 90 mmHg	≥ 20 mmHg increase ≥ 20 mmHg decrease
Diastolic Blood Pressure ^b	> 105 mmHg < 50 mmHg	≥ 15 mmHg increase ≥ 15 mmHg decrease
Orthostatic Hypotension	≥ 20 mmHg decrease in systolic blood pressure and a ≥ 25 bpm increase in heart rate from supine to sitting/standing	Not Applicable (baseline status not considered)
Weight	-	≥ 7% increase ≥ 7% decrease

^a In order to be identified as potentially clinically relevant, an on-treatment value must meet the “Criterion Value” and also represent a change from the subject’s baseline value of at least the magnitude shown in the “Change Relative to Baseline” column.

^b As defined in “Supplementary Suggestions for Preparing an Integrated Summary of Safety Information in an Original NDA Submission and for Organizing Information in Periodic Safety Updates,” FDA Division of Neuropharmacological Drug Products draft (2/27/87).

Protocol 331-201-00079

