3.2.2 Brexpiprazole + Antidepressant Treatment Dosing Regimen

Acute Treatment Phase (Phase A): Subjects will receive single-blind brexpiprazole + open-label ADT for 6 to 8 weeks. Subjects will be titrated to a target dose of brexpiprazole over a 2- to 4-week period. Thereafter, subjects who had not met response criteria as defined in the blinded addendum, did not have potentially dose-related adverse events (AEs), and had not achieved the maximum dose of medication can have their dose increased up to 3 mg. Dose decreases can occur at scheduled or unscheduled visits once a dose of 3 mg is achieved. Subjects not able to tolerate the minimum specified target dose of 2 mg/day will be discontinued. The intention of this dosing paradigm is to have subjects treated at a maximum tolerated dose of brexpiprazole during the Acute Treatment Phase to optimize an efficacious response.

No adjustments to ADT doses are allowed in Phase A without approval from the medical monitor and changes may not be made within 5 days of a change in brexpiprazole dose.

The Acute Treatment Phase dosing schedule for brexpiprazole (flexible dosing with lead-in titration) is presented in [Table 3.2.2-1](#).

Stabilization Phase (Phase B): Eligible subjects who have completed Phase A and enroll in the Stabilization Phase will receive single-blind brexpiprazole + open-label ADT for 12 weeks. Brexpiprazole dose decreases can occur at scheduled or unscheduled visits, but dose increases can occur only at scheduled visits. The dose of brexpiprazole must be stable for the last 4 weeks of the Stabilization Phase. Subjects not meeting stability criteria will be discontinued from the trial.

No adjustments to ADT doses are allowed in Phase B without approval from the medical monitor and changes may not be made within 5 days of a change in brexpiprazole dose.

No dose adjustments to the ADT are allowed in the last 4 weeks of Phase B.

Double-blind Randomized Withdrawal Phase (Phase C): Eligible subjects who have completed the Stabilization Phase will be randomized into the Double-blind Randomized Withdrawal Phase to brexpiprazole or placebo + open-label ADT in a 1:1 ratio for up to 26 weeks. Subjects randomized to brexpiprazole +ADT should maintain the doses of brexpiprazole that they were receiving at Week 20 of the Stabilization Phase. A one-time

Protocol 331-201-00079

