17.	Subjects with uncontrolled hypertension (DBP $>$ 95 mmHg) or symptomatic hypotension, or orthostatic hypotension which is defined as a decrease of \geq 30 mmHg in SBP and/or a decrease of \geq 20 mmHg in DBP after at least 3 minutes standing compared to the previous supine blood pressure, OR development of symptoms. NOTE: Blood pressure measurements may be repeated once to ensure reproducibility of the exclusionary result(s) before excluding a subject based on the criteria noted above.
18.	Subjects with known ischemic heart disease or history of myocardial infarction- or congestive heart failure (whether controlled or uncontrolled).
19.	Subjects with epilepsy or a history of seizures, except for a single seizure episode; for instance childhood febrile seizure, post traumatic, or alcohol withdrawal.
Physical and Laboratory Results	
20.	Subjects with a positive drug screen for cocaine or other drugs of abuse (excluding known prescription stimulants and other prescribed medications and marijuana). Detectable levels of alcohol, marijuana, barbiturates, or opiates in the drug screen are not exclusionary if, in the investigator's documented opinion, the subject does not meet DSM-5 criteria for moderate to severe substance use disorder and the positive test does not signal a clinical condition that would impact the safety of the subject or interpretation of the trial results, and participation is agreed to by the medical monitor prior to treatment.

Protocol 331-201-00079

Table 3.4.3-1 Exclusion Criteria

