Blood pressure and heart rate measurements will be made in the supine, sitting, and standing positions after the subject has been in each position for at least 3 minutes. The supine measurements will be performed first followed by sitting.

Subjects with uncontrolled hypertension (screening DBP > 95 mmHg in any position) or symptomatic hypotension are excluded from the trial as are subjects with orthostatic hypotension defined as a decrease of ≥ 30 mmHg in SBP and/or a decrease of

Protocol 331-201-00079

≥ 20 mmHg in DBP after at least 3 minutes standing compared to the previous supine blood pressure OR development of symptoms (see [Table 3.4.3-1](#)). In addition, subjects should be excluded if they have any other vital sign measurement at screening that, in the investigator's judgment, is medically significant in that it would impact the safety of the subject or the interpretation of the trial results. However, any abnormal screening vital sign result(s) considered to be clinically significant should be repeated to confirm the finding(s) before excluding the subject from the trial. [Appendix 2](#) is included to assist investigators in their assessments of results that may be potentially medically significant, depending on the subject's medical history and clinical presentation.

3.7.3.4 **Electrocardiogram Assessments**

All ECG recordings will be obtained after the subject has been supine and at rest for at least 5 minutes. Additional 12-lead ECGs may be obtained at the investigator's discretion and should always be obtained in the event of an electroconvulsive therapy (ECT). Electrocardiogram results will be evaluated at the investigational site to determine the subject's eligibility and to monitor safety during the trial. The principal investigator or qualified designee will review, sign, and date each ECG reading, noting whether or not any abnormal results are of clinical significance. The ECG will be repeated if any results are considered to be clinically significant. A central ECG service will be utilized for reading all ECGs in order to standardize interpretations for the safety analysis.

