1.1 Trial Design Schematic

^aScreening, baseline, and Week 6-8 visits of Phase A; Week 20 of Phase B; and Week 46 of Phase C need to be conducted in clinic

Figure 1.1-1 COVID-19 Impact Trial Design Schematic

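### Minor: the protocol's on-treatment orthostatic hypotension criterion needs a heart-rate rise and has no diastolic limb, so some asymptomatic postural falls that meet the entry definition would not be counted as vital-sign abnormalities

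*Protocol*

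**What the plan says.** **On treatment.** The orthostatic row of Protocol Appendix 2 reads "≥ 20 mmHg decrease in systolic blood pressure and a ≥ 25 bpm increase in heart rate from supine to sitting/standing". Both parts are required, diastolic pressure is not mentioned, and baseline status is not considered. Protocol 3.7.3.3 says that the appendix "is included to assist investigators in their assessments of results that may be potentially medically significant". The appendix's own footnote also applies its criteria to on-treatment values, and Protocol 7.6.3 adds: "Potentially clinically relevant results in vital signs and body weight will also be summarized".

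**At entry.** Protocol 3.7.3.3 excludes subjects with "orthostatic hypotension defined as a decrease of ≥ 30 mmHg in SBP and/or a decrease of" at least 20 mmHg in diastolic pressure. Exclusion criterion 17 (Protocol Table 3.4.3-1) has the same rule, ending "in DBP after at least 3 minutes standing compared to the previous supine blood pressure, OR development of symptoms". Neither place has a heart-rate condition. The note to criterion 17 allows one repeat reading.

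**Data and tables.** Pressure and heart rate are taken supine, sitting and standing (Protocol 3.7.3.3). SAP 5.6.3 tabulates the incidence of treatment-emergent abnormal vital signs by treatment group and lists them. For Phase A it gives only a listing of the abnormalities. For its criteria it points to the SAP's Appendix 2, whose text is not available here.

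**The concern.** The protocol treats a large postural pressure fall as reason enough to keep a subject out, whatever the heart rate does. Once the subject is on drug, the row that counts such falls also asks for a heart-rate rise of at least 25 bpm and ignores diastolic pressure. A subject could therefore have, on brexpiprazole, a fall that would have excluded them at screening and not be counted as having an abnormal vital sign.

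Safety and tolerability are the trial's secondary objective. At stake is how complete one safety table is in Phases B and C, and one listing in Phase A. Phase A matters because dosing starts there: "Subjects will be titrated to a target dose of brexpiprazole over a 2- to 4-week period". The Phase A vital-sign listing shows only readings that meet the criteria, so a fall that misses them is not picked out there either.

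**Working it through.** No figure in the plan needs reproducing. The check sets the two rules side by side and applies them to example readings.

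**Rules.** Let S and D be the supine-to-standing falls in systolic and diastolic pressure (mmHg) and H the heart-rate rise (bpm).

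- Entry pressure limbs (criterion 17; Protocol 3.7.3.3): S ≥ 30 or D ≥ 20.
- Appendix 2 orthostatic row: S ≥ 20 and H ≥ 25. The row also accepts a sitting reading.

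**Met at entry but not counted by the row:** S ≥ 30 with H < 25; D ≥ 20 with S < 20; or D ≥ 20 with H < 25.

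**Counted by the row but not met at entry:** 20 ≤ S < 30 with D < 20 and H ≥ 25. So neither rule contains the other.

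**Illustrative readings (not trial data).** The last column asks whether the standing value crosses the SBP < 90 or DBP < 50 limit in the other Appendix 2 rows.

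| | Supine to standing | H | S | D | Entry limbs | Orthostatic row | < 90 or < 50 |
|---|---|---|---|---|---|---|---|
| 1 | 140/85 to 100/75 | 15 | 40 | 10 | yes | no | no |
| 2 | 125/85 to 115/63 | 10 | 10 | 22 | yes | no | no |
| 3 | 130/80 to 108/72 | 26 | 22 | 8 | no | yes | no |
| 4 | 140/85 to 105/75 | 28 | 35 | 10 | yes | yes | no |
| 5 | 118/78 to 88/70 | 12 | 30 | 8 | yes | no | < 90 |
| 6 | 128/68 to 112/47 | 14 | 16 | 21 | yes | no | < 50 |

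Readings 1 and 2 are the gap. They meet the entry limbs but not the orthostatic row, and no pressure limit is crossed, so no pressure row flags them whatever the baseline. With an assumed supine heart rate of 70, the standing rates are 85 and 80, so the heart-rate rows (< 50 or > 120) do not flag them either.

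The heart-rate condition alone can decide the matter. A fall from 140/85 to 105/80 (S = 35, D = 5) is not counted when heart rate goes from 70 to 94 (H = 24). It is counted when heart rate goes from 70 to 95 (H = 25).

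**How far the other rows help**, assuming they are applied to standing values (the documents do not say which position is used):

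- A 30 mmHg systolic fall ends below 90 only from a supine value below 90 + 30 = 120.
- A 40 mmHg systolic fall ends below 90 only from below 90 + 40 = 130.
- A 20 mmHg diastolic fall ends below 50 only from below 50 + 20 = 70.

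Each row also needs a decrease from baseline (at least 20 mmHg systolic, at least 15 mmHg diastolic). Readings 5 and 6 are therefore flagged only if that condition holds too.

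**Number missed.** It cannot be computed. The documents give no data on postural falls or on the heart-rate response to them.

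**The case against.** **The SAP's Appendix 2 cannot be seen.** This stands, and the point is conditional for that reason. The SAP does depart from the protocol elsewhere: it adds QTcN, and its Phase C Efficacy Sample no longer requires a post-randomization evaluation. A different orthostatic row is possible.

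**Entry and on-treatment cut-offs differ by design.** They do: DBP > 95 against > 105 mmHg; AST/ALT > 2 against ≥ 3 times ULN; haemoglobin ≤ 9 against ≤ 11.5 (men) or ≤ 9.5 g/dL (women); female QTcF ≥ 470 against ≥ 450 msec. A reader might infer from the orthostatic pair that the protocol contradicts itself. It does not, because screening and on-treatment flagging are different tasks. But those other pairs mostly move a threshold on one measure. The orthostatic row adds a condition on another measure and drops a limb, which changes the kind of event counted.

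**Other outputs cover it.** In part. Symptomatic cases may be reported as adverse events, and treatment-emergent events are tabulated by preferred term in Phases B and C (Protocol 7.6.1.2 and 7.6.1.3; SAP 5.6.1). It would therefore be wrong to infer that the row is the trial's only count of orthostatic hypotension. The planned Phase B and C vital-sign listings may also let individual falls be recovered, if readings are shown by position. What remains is asymptomatic falls above the absolute limits. Group summaries of change from baseline do not count those subjects.

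**The COVID-19 addendum.** A reader might also cite its optional vital signs at remote visits as part of the fault. Fewer readings reduce the yield of any orthostatic definition, so this says nothing against this row.

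**A new row needs a baseline rule.** Correct. SAP 5.6.3 tabulates treatment-emergent results, and without a rule a subject with the same fall at Week 20 would count in Phase C. The fix supplies one.

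**Conclusion.** The point holds as a minor gap in capture. As Protocol Appendix 2 is written, some asymptomatic postural falls that satisfy the protocol's own entry pressure limbs would not be counted as vital-sign abnormalities on treatment. The gap reaches the SAP 5.6.3 incidence table only on the assumption that the SAP's Appendix 2 repeats the protocol row.

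Its size is unknown. The documents do not support a claim that any subject, arm comparison or safety conclusion would change. In Phase C the subjects have already tolerated the drug through Phases A and B, which limits the likely effect further. The primary analysis and the stopping boundaries are not involved. This is an optional improvement, worth making because it is cheap.

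**What to change.** Keep the existing orthostatic row. In SAP 5.6.3 add one incidence row, for Phase B and by arm for Phase C:

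- **Event:** supine-to-standing systolic fall of at least 30 mmHg and/or diastolic fall of at least 20 mmHg, regardless of heart rate.
- **Denominator:** subjects with at least one on-treatment pair of supine and standing readings in that phase. This follows the ECG rule in SAP 5.6.4, which counts only patients with an on-treatment evaluation.
- **Baseline rule, stated explicitly:** either baseline status is not considered, as in the existing row, or the fall counts as treatment-emergent only if absent at the phase baseline. The second is closer to the wording of SAP 5.6.3.

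Add the same flag to the Phase A listing, since titration takes place there. Symptoms stay in adverse-event reporting.

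**Cost:** SAP wording, one table row and one listing flag, all from positional readings already collected. The downside is a somewhat higher reported incidence that rests on unconfirmed single readings, which a footnote to the table should say.
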